6.3 Definition of On-Treatment Period

An on-treatment period is defined as the time from the first dose of study treatment until the end of treatment safety follow-up (4 weeks \pm 7 days from the last dose of study drug, i.e., until 35 days from the last dose) or end of the study, whichever occurs first.

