6.4 Definition of an Extended On-Treatment Period

An extended on-treatment period (follow-up) is defined as the time from the first dose of study treatment through 90 days after the last dose of study treatment or end of the study, whichever

occurs first. This is used for reporting immune-related AEs and cluster terms and also as a sensitivity analysis for reporting all treatment-emergent adverse events.

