8.1 General Statistical Procedures

Frequency distributions for categorical variables will be provided as number of subjects in the category and the percentages of the total number of subjects in the given population as noted. Counts of missing observations will be included in the denominator and presented as a separate category. Percentages will be reported to one decimal place.

A 2-sided 95% Wilson score confidence interval (CI) for categorical variables without multiplicity adjustment will be provided where appropriate for efficacy analysis.

The descriptive statistics for continuous variables will be number of subjects, mean, standard deviation, median, minimum, and maximum. Mean and median will be reported to 1 more decimal place than the raw data, while the standard deviation will be reported to 2 more decimal places than the raw data. Minimum and maximum will be reported the same as the original data.

All listings (with the exception of All Subject listings) will be performed using the Safety Analysis Set and sorted by subject ID and, if applicable, by visit date unless otherwise specified.

The study drug name may be abbreviated in TLFs as "Zal" for zalifrelimab (AGEN1884).

Time intervals (in days), unless specified otherwise, will be calculated as difference between ending and start day + 1 day. For conversion to months, interval days will be divided by 30.4375.

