8.6.1 Drug Exposure

Overall drug exposure will be summarized in Safety Analysis Set by the following parameters:

- Duration of treatment (week), calculated as: (last dose date first dose date + 1)/7
- Number of treatment infusions received
- Total cumulative dose (mg), defined as the sum of the actual doses (mg) taken
- Dose compliance, defined as percentage of actual dose taken relative to planned dose
- Planned/actual dose intensity for the first 4 cycles, defined as total planned or actual dose from the first 4 cycles (mg) divided by actual duration of the first 4 cycles (weeks)

Note: if patients permanently withdraw from the treatment before Cycle 4 due to reasons other than disease progression or death, the remaining cycles will be calculated with planned length, i.e., 3 weeks, and zero dose. If patients withdraw from the treatment due to disease progression or death, the number of cycles actually completed will be used.

- Number of doses with infusion related reactions (as reported on drug administration eCRFs)
- Number of subjects with at least one infusion related reaction
- Number of subjects with any dose interrupted/not completed
- Number of doses interrupted/not completed
- Occurrences and number of actual doses exceeding adjusted planned dose by more than 5% (adjusting for up to 10 % weight loss.)

Per pharmacy manual, no adjustment in dose was required for body weight changes within 10%, therefore dose exceeding planned dose by > 5% will be interpreted as any dose 5% greater than the highest daily dose prescribed by the clinical trial protocol, after accounting for up to 10% changes due to decrease in body weight. Adjusted planned dose is calculated by multiplying prescribed dose level by adjusted weight W_{adj} . Denoting by W_0 and W_{adj} the baseline and the most recent weights, adjusted weight is: $W_{adj} = W$ for $W \ge W_0$ and $W_{adj} = \min(W_0, 1.1 \times W)$ for $W < W_0$.

Missing weight measurements in drug exposure analysis will be imputed by last observation carried forward, multiple measurements for the same timepoint will be averaged.

Confidential Page 20 of 30

Details of study treatment exposure will be listed for Safety Analysis Set.

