- Other AEs of special interest determined by investigators

Unless otherwise stated, the number of subjects with an event (subject-wise) and the number of events (event-wise) will be provided for each summary.

Immune-related AEs will be tabulated using investigator-reported irAEs.

Confidential Page 21 of 30

Agenus Inc. Statistical Analysis Plan for Study C-500-01 Phase 2

Infusion related AEs will be tabulated using infusion-related reactions as reported by the investigators.

The following summaries by either SOC and PT or by PT and by severity grade will be provided. Summaries will be sorted by decreasing incidence of PT (within SOC, if applicable).

- TEAEs by SOC and PT, and by PT
- TEAEs by relationship to study drug, severity grade, SOC, and PT
- Drug-related TEAEs by SOC and PT, and by PT
- TEAEs leading to permanent treatment discontinuation by PT
- TEAEs leading to death by PT
- Drug-related TEAEs leading to permanent treatment discontinuation by PT
- Drug-related TEAEs leading to death by PT
- Serious TEAEs by SOC and PT, and by PT
- Serious TEAEs by relationship to study drug and severity grade, by SOC and PT
- Drug related serious TEAEs by SOC and PT, and by PT
- irAEs by SOC and PT, and by PT
- irAEs by severity grade, SOC, and PT
- Infusion-related TEAEs by SOC and PT, and by PT
- Infusion-related TEAEs by severity grade, SOC, and PT
- Laboratory abnormalities worsening (in at least one on-study measurement, relative to baseline) by NCI-CTCAE version 5 criteria.
- Alanine aminotransferase (ALT), aspartate aminotransferase (AST), or bilirubin normal at baseline but with elevations $\geq 2 \times \text{upper limit of normal (ULN)}$

The overall summary of TEAEs will be reported by age (age < 55 vs age \geq 55, age < 65 vs age \geq 65, and age < 75 vs age \geq 75), by race group including at least 5 subjects (groups with < 5 subjects will be reported summarily as "Other"), by normal vs abnormal creatinine and bilirubin levels at baseline, and by drug manufacturing process. Subgroup analyses will be provided for HCC patients, non-HCC and PD-1/PD-L1 refractory patients, and non-HCC and PD-1/PD-L1 naïve patients.

In addition, the overall summary of AE incidence per month of drug exposure will be presented. Such a summary will report #patients/(total time of exposure in months) and #AEs/(total time of exposure in months.)

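### The SAP's patient-level AE rate per month keeps exposure after the first event in the denominator, so for rows where most subjects have an event it mainly tracks treatment duration

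*SAP*

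**What the plan says.** SAP 8.6.2 states that "the overall summary of AE incidence per month of drug exposure will be presented". It gives two rates over one denominator. The patient-level rate is "Such a summary will report #patients/(total time of exposure in months"; the event-level rate is "AEs/(total time of exposure in months". Nothing in the section stops a subject's time at the first event, and total time of exposure is not defined.

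The nearest definition is in SAP 8.6.1: "Duration of treatment (week), calculated as: (last dose date first dose date + 1)/7", that is, last dose date minus first dose date plus one day, in weeks. On that clock a subject who receives one dose contributes one day.

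The AE windows are longer. The on-treatment period in SAP 6.3 runs "until 35 days from the last dose". The extended period in SAP 6.4, used for immune-related AEs and for a sensitivity analysis of all treatment-emergent AEs, runs "through 90 days after the last dose of study treatment".

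The rate is an addition to the ordinary counts. SAP 8.6.2 also says that "the number of subjects with an event (subject-wise) and the number of events (event-wise) will be provided for each summary".

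**The concern.** The numerator and denominator of the patient-level rate belong to different quantities. After a first event the subject can add nothing more to the numerator but keeps adding time to the denominator. When nearly everyone has an event, the rate approaches N divided by total exposure, which is one over mean exposure whatever the underlying hazard.

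Total time does suit the event-level rate, because a subject can have further events. The objection about time after the first event is confined to the patient-level line.

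Safety is a primary endpoint, and the SAP labels this figure an incidence per month. A reader may take it as a risk rate and compare it with rates from other series that had different treatment durations.

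**Working it through.** **Inputs.** Neither document states an AE rate, an AE frequency or an exposure total, so there is no planned figure to reproduce. From the documents:
- four doses at 3-week intervals, then continuation every 3, 6 or 12 weeks, for at most 1 year (SAP 3.1)
- AE windows ending 35 or 90 days after last dose (SAP 6.3, 6.4)
- duration from first to last dose plus one day (SAP 8.6.1)
- the month conversion, "For conversion to months, interval days will be divided by 30.4375" (SAP 8.1)

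Assumed: a constant hazard, the exposure patterns below, treatment-emergent AEs in the numerator, and the 8.6.1 duration as exposure.

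**Step 1: equal exposure T, AE window equal to exposure.** With hazard h, the proportion with an event is p = 1 - exp(-hT).
- SAP rate = Np / (NT) = p/T.
- First-event rate = Np / (summed time to first event or T) = h = -ln(1-p)/T.
- Ratio of SAP rate to first-event rate = p / (-ln(1-p)).

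| p | 10% | 20% | 30% | 50% | 80% | 90% | 95% |
|---|---|---|---|---|---|---|---|
| Ratio | 0.95 | 0.90 | 0.84 | 0.72 | 0.50 | 0.39 | 0.32 |

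The understatement is 10-16% at 20-30% incidence. At 95% it is 1/0.317, or about 3.2-fold.

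**Step 2: the 95% case in months.** Four doses span 3 × 21 + 1 = 64 days, and 64/30.4375 = 2.10 months.

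| T (months) | SAP rate | First-event rate |
|---|---|---|
| 2.10 | 0.452 | 1.425 |
| 6 | 0.158 | 0.499 |
| 12 | 0.079 | 0.250 |

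Both columns fall 5.7-fold from top to bottom, because p is held fixed. That fall is not itself the distortion; the gap within each row is.

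**Step 3: the same hazard, different durations.** I used simulated exposure patterns (400,000 subjects each), with doses every 3 weeks and exposure of (k-1) × 21 + 1 days for k doses. The percentages of subjects receiving each number of doses were:

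| Pattern | 1 | 2 | 3 | 4 | 6 | 9 | 17 | Mean exposure (months) |
|---|---|---|---|---|---|---|---|---|
| Short | 20 | 30 | 20 | 20 | 5 | 3 | 2 | 1.5 |
| Medium | 10 | 15 | 10 | 25 | 15 | 15 | 10 | 3.2 |
| Long | 0 | 0 | 0 | 20 | 20 | 30 | 30 | 6.1 |

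With a true rate of 1.0 per month and matching windows, the SAP formula returns 0.394, 0.238 and 0.159. The first-event rate returns 1.00 each time. Duration alone produces the spread. Unequal exposure also widens the gap at moderate incidence: in the short pattern at 22% incidence the ratio is 0.75, or 25% too low.

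**Step 4: the SAP's own windows.** Exposure stops at last dose, while AEs count for 35 or 90 days more. Ratio of SAP rate to first-event rate, with incidence in brackets:

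| Pattern, tail | Results |
|---|---|
| Short, 35 days | 1.62 (12%), 1.28 (38%), 0.90 (67%), 0.58 (87%), 0.33 (97%) |
| Short, 90 days | 1.91 (57%), 1.17 (87%), 0.66 (98%) |
| Medium, 35 days | 0.80 (52%), 0.29 (93%) |
| Long, 35 days | 0.58 (71%), 0.30 (93%) |

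**Step 5: closed-form check of the reversal.** Take exposure E as exponential with mean parameter 2 months, capped at 12, and a true rate of 0.1 per month.
- Mean exposure = 2(1 - exp(-6)) = 1.995 months.
- E[exp(-0.1E)] = (0.5/0.6)(1 - exp(-7.2)) + exp(-7.2) = 0.833.
- Matching windows: (1 - 0.833)/1.995 = 0.083, which is 17% too low.
- With the tail of 35/30.4375 = 1.15 months: (1 - 0.833 × exp(-0.115))/1.995 = 0.257/1.995 = 0.129, which is 29% too high.

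**The case against.** Four points count against giving this much weight, and most of each stands.

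- **Subgroups.** A reader might infer that the rate distorts comparison of the HCC, PD-1/PD-L1-refractory and PD-1/PD-L1-naive groups. The SAP does not support that. It assigns those breakdowns to the summary and subgroup analyses of treatment-emergent AEs, and introduces the monthly rate afterwards without naming any split. The distortion is a risk only if the rate is split or compared.
- **Direction.** A reader might also infer that rates for common AEs are far too low in general. Steps 1 and 4 do not support that. The shortfall is modest at 20-30% incidence with equal exposure and matching windows, and the longer AE windows can turn it into an excess. But the two opposing errors do not make the rate valid. In the short pattern with a 35-day tail the ratio runs from 1.62 to 0.33 as incidence rises, so the error changes sign with event frequency.
- **Constant hazard.** The first-event rate recovers the true value in Step 3 because the hazard was set constant. Protocol 3.1 describes both early and late immune toxicity. Under a changing hazard the first-event rate also depends on length of follow-up. It still matches its numerator to time at risk, which the SAP formula does not.
- **Consequence.** The table is descriptive, crude subject and event counts accompany it, time to onset is summarised separately for immune-related AEs, and no decision rule uses the rate. This limits the severity but does not repair the formula.

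**Conclusion.** The point holds in a limited form. As written, the patient-level figure is not an incidence per month at risk. For rows where most subjects have an event it tends towards one over mean exposure, and it is about 3.2-fold below the first-event rate at 95% incidence. At 20-30% incidence the shortfall is about 10-16%. These figures assume a constant hazard, equal exposure and matching windows.

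If exposure is the 8.6.1 duration, the 35- and 90-day AE windows push the other way, and the net error can shrink or reverse when treatment is short. The actual size cannot be known from the documents, because they give neither AE frequencies nor an exposure distribution. The harm is confined to one descriptive safety table, so this is a minor correction.

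**What to change.** In SAP 8.6.2:
- Define the patient-level rate as subjects with a first event divided by the summed time from first dose to first event or, for subjects without one, to the end of the AE window used for the numerator (on-treatment or extended).
- For the event-level rate, keep each subject's full time over that same window, not cut at the first event.
- Define total time of exposure accordingly, and state which AEs and which window each row uses.

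The cost is a few sentences and one derived time variable. Onset dates are already collected, and the SAP already derives time to onset for immune-related AEs. One side effect needs a footnote: SAP 6.6 sets some partial or missing onset dates to the first dose date, which shortens time at risk, so the number of such dates should be shown.

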4.3 Management of Immune-Related Adverse Events

Immuno-oncology agents such as AGEN1884 are associated with immune-related adverse events (irAEs). Early recognition and management of irAEs may mitigate severe toxicity. Investigators should also monitor subjects closely for potential irAEs, which may manifest after weeks of treatment, at the earliest. Such events may consist of persistent rash, diarrhea, colitis, autoimmune hepatitis, pneumonitis, encephalitis, arthritis, glomerulonephritis, cardiomyopathy, or uveitis and other inflammatory eye conditions.

Management algorithms have been developed to assist investigators in assessing and managing the following groups of irAEs: gastrointestinal, pulmonary, dermatological, renal, hepatic, neurological, and endocrine, among others.

Adverse events (both non-serious and serious) associated with drug exposure and consistent with an immune phenomenon may represent an immunologic etiology. These irAEs may be predicted based on the nature of the study drugs, their mechanism of action, and reported experience with immunotherapies that have a similar mechanism of action. An irAE can occur shortly after the first dose or several months after the last dose of treatment. Particular attention should be paid to AEs that may be suggestive of potential irAEs, as outlined below.

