4.3.4 Hepatic irAEs

Rule out non-inflammatory causes (e.g., alcohol use, acute viral hepatitis, flare up from chronic hepatitis, co-infection [e.g., with hepatitis D], etc.). If a non-inflammatory cause is identified, treat accordingly and continue therapy per protocol. Consider imaging for obstruction and a hepatologist consult (Table 6).

Table 6: Hepatic ir AE Management Algorithm

	Hepatic irAEs										
CTCAE Grade of Liver Test Elevation	Management	Follow-Up									
Grade 1 AST or ALT >ULN to 3 x ULN and/or total bilirubin >ULN to 1.5 x ULN.	Continue AGEN1884 therapy per protocol.	 Continue liver function tests (LFT) monitoring per protocol. If worsens: Treat as grade 2 or grade 3-4. 									
Grade 2 AST or ALT >3 to ≤5 x ULN and/or total bilirubin >1.5 to ≤3 x ULN. If subject has concurrent AST or ALT >3 x ULN and total bilirubin >2 x ULN, discontinue AGEN1884 therapy per protocol (Hy's Law)	 Delay AGEN1884 therapy per protocol. Increase frequency of monitoring to every 3 days. 	If returns to baseline: Resume routine monitoring; resume AGEN1884 therapy per protocol. If elevations persist >5 to 7 days or worsen: 0.5-1 mg/kg/day methylprednisolone IV or oral equivalent. When LFT returns to grade 1 or baseline, taper corticosteroids over ≥1 month, consider prophylactic antibiotics for opportunistic infections, and resume AGEN1884 therapy per protocol.									
Grade 3-4 AST or ALT >5 x ULN and/or total bilirubin >3 x ULN.	 Permanently discontinue AGEN1884 therapy per protocol. Increase frequency of monitoring to every 1-2 days. 1-2 mg/kg/day methylprednisolone IV or oral equivalent.* Add prophylactic antibiotics for opportunistic infections. Consult gastroenterology. Consider obtaining MRI/CT scan of liver and liver biopsy if clinically warranted. 	 If returns to grade 2: Taper corticosteroids around 4 to 6 weeks. If does not improve in >3 to 5 days, worsens, or rebounds: Add mycophenolate mofetil 1 g twice daily. If no response within an additional 3-5 days, consider other immunosuppressants per local guidelines. 									

Confidential Page 41 of 78

	Hepatic irAEs	
CTCAE Grade of Liver Test Elevation	Management	Follow-Up

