4.3.6 Renal irAEs

Rule out non-inflammatory causes. If non-inflammatory cause is identified, treat accordingly and continue therapy per protocol (Table 8).

Table 8: Renal ir AE Management Algorithm

	Renal irAEs										
CTCAE Grade of Creatinine Elevation	Management	Follow-Up									
Grade 1 Creatinine >ULN and >baseline but ≤1.5 x baseline	 Continue AGEN1884 therapy per protocol. Monitor creatinine weekly. 	 If returns to baseline: Resume routine creatinine monitoring per protocol. If worsens: Treat as grade 2 or grade 3-4. 									
Grade 2-3 Creatinine >1.5 x baseline to ≤6 x ULN	 Delay AGEN1884 therapy per protocol. Monitor creatinine every 2-3 days. 0.5-1.0 mg/kg/day methylprednisolone IV or oral equivalent. Consider renal biopsy 	 If returns to grade 1: Taper corticosteroids over ≥1 month, consider prophylactic antibiotics for opportunistic infections, and resume AGEN1884 therapy and routine creatinine monitoring per protocol. If elevations persist > 7 days or worsen: Treat as grade 4. 									
Grade 4 Creatinine >6 x ULN	 Discontinue AGEN1884 therapy per protocol. Monitor creatinine daily. 1.0-2.0 mg/kg/day methylprednisolone IV or IV equivalent. Consult nephrologist. Consider renal biopsy. 	If returns to grade 1: Taper corticosteroids over ≥1 month and add prophylactic antibiotics for opportunistic infections.									

CTCAE: Common Terminology Criteria for Adverse Events; irAE: immune-related adverse event; IV: intravenous; kg: kilogram; mg: milligram; ULN: upper limit of normal.

Confidential Page 44 of 78

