5.8.6.1.2 Immune-Related Adverse Events

Blocking CTLA-4 function may permit the emergence of immune-mediated AEs that result in clinical syndromes resembling autoimmunity. Rash/vitiligo, diarrhea/colitis, uveitis/episcleritis, hepatitis, and hypopituitarism were drug-related, presumptive immune-related events noted in previous studies of anti–CTLA-4 agents.

For the purposes of this study, an irAE is defined as an adverse event of unknown etiology, associated with drug exposure, and is consistent with an immune phenomenon. Efforts should be made to rule out neoplastic, infectious, metabolic, toxin, or other etiologic causes prior to labeling an adverse event an irAE. Serological, immunological, and histological (biopsy) data should be used to support the diagnosis of an immune-mediated toxicity.

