The analysis of irAEs in the above summaries will be performed using data as reported by investigators (the primary analysis). In addition, as an exploratory analysis, TEAEs using sponsor's definition of irAEs, will be summarized. If an AE falls within any of the cluster terms listed below, it will be considered as an irAE by sponsor's definition. For each irAE, the summary will include median time (and range) to onset, median duration (and range) in days of

Confidential Page 22 of 30

the first instance of such AE per patient. Finally, descriptive statistics will be provided for time of onset, cycle of onset, and cumulative dose at onset of first irAE by SOC.

If an SOC or PT was reported more than once for a subject, the subject would only be counted once in the incidence for that SOC or PT.

In tabulation by severity grade:

- For a given SOC, only the most severe SOC for each subject will be included
- For a given PT, only the most severe PT for each subject will be included

In addition, TEAEs (evaluated within the extended treatment period) will be reported for the following clusters of immune-mediated AEs: pneumonitis, colitis, diarrhea, hepatitis, hypothyroidism, hyperthyroidism, thyroiditis, hypophysitis, adrenal insufficiency, diabetes, nephritis, rash, pruritus, and other immune-related AEs. These clusters will be defined by the following MedDRA version 22.1 Preferred Terms:

- **Pneumonitis**: interstitial lung disease; pneumonitis; acute interstitial pneumonitis; immune-mediated pneumonitis
- Colitis: allergic colitis, autoimmune colitis, colitis, colitis erosive, colitis microscopic, enterocolitis hemorrhagic, eosinophilic colitis, necrotizing colitis, neutropenic colitis, enterocolitis, immune-mediated enterocolitis,
- Diarrhea: diarrhoea, diarrhoea hemorrhagic
- **Hepatitis:** acute hepatic failure, autoimmune hepatitis, hepatic failure, hepatitis, hepatitis acute, hepatoxicity, liver injury, hepatocellular injury, immune-mediated hepatitis, immune-mediated hepatic disorder, drug-induced liver injury
- **Hypothyroidism:** autoimmune hypothyroidism, hypothyroid goiter, hypothyroidism, immune-mediated hypothyroidism, myxoedema, thyroid atrophy
- **Hyperthyroidism**: Basedow's disease, hyperthyroidism, Marine Lenhart syndrome, primary hyperthyroidism, immune-mediated hyperthyroidism, secondary hyperthyroidism, tertiary hyperthyroidism, thyroid dermatopathy, thyroid crisis, thyrotoxic periodic paralysis, toxic goiter, toxic nodular goiter,

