- **Thyroiditis**: autoimmune thyroiditis, thyroiditis, thyroid acute, thyroiditis chronic, thyroiditis fibrous chronic, thyroiditis subacute, immune-mediated thyroiditis
- Hypophysitis: hypophysitis, lymphocytic hypophysitis, hypopituitarism
- Adrenal insufficiency: Addison's disease, adrenal androgen deficiency, adrenal insufficiency, adrenal suppression, adrenocortical insufficiency acute, glucocorticoid deficiency, hypoaldosteronism, mineralocorticoid deficiency,
- **Diabetes** without prior history: type 1 diabetes mellitus, diabetes mellitus, latent autoimmune diabetes in adults, diabetic ketoacidosis, and hyperosmolar coma
- **Nephritis**: autoimmune nephritis, lupus nephritis, nephritis hemorrhagic, immune-mediated nephritis

Confidential Page 23 of 30

- Rash: pemphigoid, rash, rash erythematous, rash generalized, rash macular, rash maculopapular, rash pruritic, rash papular, immune-mediated dermatitis
- Pruritus: pruritus, pruritus allergic, pruritus generalized
- Other Immune-related AEs: myocarditis, immune-mediated myocarditis, uveitis, immune-mediated uveitis, iritis, vitiligo, psoriasis, myositis, immune-mediated myositis, rheumatoid arthritis, systemic inflammatory response syndrome, sarcoidosis, autoimmune disorder, meningitis, encephalitis, encephalitis autoimmune, immune-mediated encephalitis, encephalopathy, autoimmune encephalopathy, immune-mediated encephalopathy, Guillain-Barre syndrome, myasthenia gravis, demyelination, stomatitis, pancreatitis, autoimmune pancreatitis, pancreatitis acute, immune-mediated pancreatitis, immune-mediated gastritis, lichen planus, colitis ulcerative, Crohn's disease, inflammatory bowel disease, hemolytic anemia, immune-thrombocytopenia, immune thrombocytopenic purpura, aplastic anemia, bicytopenia, pancytopenia, immune-mediated pancytopenia

For each cluster, the analysis will summarize: the total incidence and number of all TEAEs included in the cluster and by severity grade, % of pts who received treatment with pituitary and hypothalamic hormones and analogues, with corticosteroids for systemic use, or with thyroid therapy (concomitant medications in, respectively, H01, H02, or H03 ATC2 groups indicated for AE and started following AE onset but no later than the date of AE resolution or 21 days from AE onset, whichever comes earlier), % leading to dose hold, % leading to drug discontinuation, % resolved, time to onset of first TEAE and duration of all TEAEs and TEAEs of grade ≥ 3.

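### The closed term list behind the exploratory sponsor-defined irAEs omits four conditions the protocol names as possible irAEs, and plain nephritis

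*SAP*

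**What the plan says.** SAP 8.6.2 plans two irAE analyses. The primary one uses events that investigators report as irAEs. The exploratory one uses a sponsor definition: "If an AE falls within any of the cluster terms listed below, it will be considered as an irAE by sponsor's definition". The clusters are fixed by named MedDRA version 22.1 preferred terms, and the residual cluster of other immune-related AEs is also a term list. The nephritis cluster has four entries: "autoimmune nephritis, lupus nephritis, nephritis hemorrhagic" and the immune-mediated form.

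For each cluster the SAP reports incidence and grade, the percentage treated with systemic corticosteroids, pituitary or hypothalamic hormones, or thyroid therapy, the percentages leading to dose hold, leading to discontinuation and resolved, and time to onset and duration.

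The protocol gives its own examples. Section 4.3 lists possible irAEs, ending with "encephalitis, arthritis, glomerulonephritis, cardiomyopathy, or uveitis and other inflammatory eye conditions". Section 5.8.6.1.2, on events noted with earlier anti-CTLA-4 agents, lists "Rash/vitiligo, diarrhea/colitis, uveitis/episcleritis, hepatitis, and hypopituitarism". Tables 6 and 8 manage hepatic and renal irAEs by laboratory grade, under the column titles "CTCAE Grade of Liver Test Elevation" and "CTCAE Grade of Creatinine Elevation".

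**The concern.** A closed list is reproducible, but it finds only what is on it. If the protocol tells investigators to watch for a condition as a possible irAE and the SAP list has no term for it, that condition gets no cluster row, whether or not the investigator flags it.

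What would be lost is specific. The cluster tables are where the SAP plans to show, by type of immune toxicity, how often steroids or hormones were used, how often dosing was held and how often the event resolved. No other planned table gives those three by toxicity. The sponsor definition is also the only planned identification of irAEs that does not depend on the investigator's label. Safety is a primary endpoint (SAP 4.4), so gaps that arise from the term list alone are worth closing.

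**Working it through.** No sample size, power or event figure is involved, so the check is a comparison of lists.

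**1. The SAP list.** Terms per cluster: pneumonitis 4, colitis 11, diarrhea 2, hepatitis 11, hypothyroidism 6, hyperthyroidism 12, thyroiditis 7, hypophysitis 3, adrenal insufficiency 8, diabetes 5, nephritis 4, rash 9, pruritus 3, other 40. The sum over 14 clusters is 125.

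**2. The protocol's named conditions against that list.**

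| Condition | Protocol section | On the SAP list? |
|---|---|---|
| Rash, diarrhea, colitis, hepatitis, uveitis | 4.3 and 5.8.6.1.2 | Yes |
| Pneumonitis, encephalitis | 4.3 | Yes |
| Vitiligo, hypopituitarism | 5.8.6.1.2 | Yes |
| Arthritis | 4.3 | No; only rheumatoid arthritis |
| Glomerulonephritis | 4.3 | No |
| Cardiomyopathy | 4.3 | No; nearest is myocarditis |
| Episcleritis | 5.8.6.1.2 | No; nearest are uveitis and iritis |

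This gives 5 + 2 + 2 = 9 present and 4 absent, out of 13 distinct conditions. Within 4.3 alone, 3 of 10 are absent.

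**3. Internal consistency.** The colitis, hepatitis, pneumonitis and thyroiditis clusters each contain their own unqualified term. The nephritis cluster does not: all 4 entries carry a qualifier.

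**4. Spelling.** The hepatitis cluster has *hepatoxicity*, while the SAP writes *hepatotoxicity* in its abbreviation list and in 8.6.4. The thyroiditis cluster has *thyroid acute* in a run of thyroiditis terms, directly before *thyroiditis chronic*.

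**5. Laboratory terms.** No listed term contains alanine, aspartate, transaminase, bilirubin or creatinine.

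**6. Following one event.** Take an AE coded as arthritis.
- Onset day 20 after the last dose, not flagged as immune-related: within the 35-day on-treatment period, so it is in the main TEAE tables, but in no cluster and not a sponsor-defined irAE.
- Onset day 60, not flagged: since 35 < 60 ≤ 90, it is outside the main TEAE tables. It is in the 90-day TEAE sensitivity analysis (SAP 6.4, 8.6.2) and in the listing of AEs between the two period ends. It is again in no cluster.
- Flagged by the investigator, either day: in the primary irAE tables, which use the 90-day period, but still in no cluster.

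**The case against.** The strongest reply is that little depends on this list. The sponsor-definition analysis is labelled exploratory, and the primary irAE tables do not use the list. Protocol 4.3 is illustrative, and only episcleritis among the four absent conditions is recorded there or in 5.8.6.1.2 as seen with earlier anti-CTLA-4 agents. All of that stands, and it limits the weight of the point. It does not explain why nine named conditions are listed and four are not.

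A reader might infer more than the documents support:

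- *That irAEs are under-counted overall.* The clusters count listed terms whatever the cause, including diarrhoea, hepatic failure, encephalopathy, stomatitis and pancytopenia. Omissions lower the sponsor-defined total and non-specific terms raise it, so the net direction is unknown.
- *That late events are lost.* The 90-day sensitivity analysis and the separate listing retain them.
- *That discontinuations are shown only by cluster.* TEAEs leading to permanent discontinuation are also tabulated by preferred term.
- *That leaving out laboratory terms is an error.* Tables 6 and 8 are management algorithms; the irAE definition in 5.8.6.1.2 asks for other causes to be ruled out. Liver tests and creatinine have shift tables, liver tests also have the 2 × ULN summary and the eDISH plot, and any elevated liver test is an AESI. About 20 HCC subjects are planned, and they may enter with AST and ALT up to 5 × ULN, so keeping bare liver-test terms out of an immune cluster is defensible. What those displays lack is a link to steroid use, holds and resolution.
- *That the misspelled entries will certainly fail to match.* That depends on programming the documents do not show.

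**Conclusion.** The point holds as a gap in an exploratory but useful set of tables. Followed as written, the list excludes 4 of the 13 conditions named in Protocol 4.3 and 5.8.6.1.2, and unqualified nephritis. Two further entries may not match coded data. The effect is confined to the cluster tables and the sponsor-defined irAE summaries; the investigator-reported irAE tables, general TEAE tables and laboratory displays do not change.

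The number of events involved cannot be estimated, because the documents give no event counts. The conclusion assumes that the list is applied as a closed set, as 8.6.2 states, and that the absent conditions can be coded to preferred terms of their own in MedDRA 22.1. The dictionary is not in the documents, so that needs a check.

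**What to change.** Before lock, in SAP 8.6.2:

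1. Add arthritis, glomerulonephritis, nephritis, cardiomyopathy and episcleritis to the appropriate clusters.
2. Replace *hepatoxicity* and *thyroid acute* with the MedDRA 22.1 spelling of the intended terms.
3. Optionally, because Tables 6 and 8 grade hepatic and renal irAEs by laboratory value, show AEs of increased liver tests and increased creatinine with the same cluster statistics on separate supplementary rows, split by HCC and non-HCC. Keep these rows out of the sponsor-defined irAE total. Do not select them on steroid treatment, which would build in the steroid percentage being reported, or on investigator-assessed relatedness, which would bring the investigator's judgement back into a definition that otherwise does without it.

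The cost is a term-list edit and a small amount of reprogramming on coded data. Sponsor-defined irAE counts may rise slightly, and some added events may have non-immune causes, as with the non-specific terms already listed. Trial conduct does not change.
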